3. Discomfort (pain) level using a 10-point visual analog scale will also be recorded after each benign pigmented lesion clearance treatment– by Numerical Scale Response (NSR), according to Appendix IIIAppendix III - Pain assessment.

STUDY POPULATION

Number of Subjects

This study will be comprised of up to 120 subjects in up to ten (10) investigational sites. Subjects who meet all the inclusion and none of the exclusion criteria will be enroll.

Subject Withdrawal and Replacement

Subjects enrolled in the study can discontinue their participation at any time for any reason without prejudice or reduction in the quality of their medical care. The investigators or sponsor can terminate a subject's participation in this study to protect the subject's health or if the subject fails to follow directions resulting in noncompliance to study procedures. Subjects who withdraw or are terminated from the study may be replaced to ensure at least 120 subjects have completed the study. Subjects who fail to complete the treatment will be replaced and will not be evaluable.

Inclusion Criteria

A subject is eligible to participate in the study if he/she meets all the following inclusion criteria:

1. Signed informed consent to participate in the study.
2. Female and male subjects, ≥ 18 and ≤ 60 years of age at the time of enrolment
3. Fitzpatrick Skin Type I to VI.
4. Abdominal fat thickness of at least 1.5 cm (measured by calibrated caliper).
5. BMI interval: $22 \leq \text{BMI} \leq 30$ (normal to overweight, but not obese).
6. If female, not pregnant, lactating and must be either post-menopausal, surgically sterilized, or using a medically acceptable form of birth control at least 3 months prior to enrollment (i.e., oral contraceptives, contraceptive implant, barrier methods with spermicide or abstinence).

 Syneron Medical Ltd. Confidential	Clinical Study to Evaluate the Safety and Efficacy of the UltraShape Power Device Using the U-Sculpt Power Transducer for Abdominal Fat and Circumference Reduction			
	Protocol #	DHF21621	Rev. Date	April 05, 2016

7. In addition, negative urine pregnancy test as tested before each treatment and at the last visit for women with bearing potential (e.g. not menopause).
8. General good health confirmed by medical history and skin examination of the treated area.
9. Willing to follow the treatment and follow-up schedule and post-treatment care instructions.

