10. Willingness to refrain from a change in diet/ exercise/medication regimen for the entire course of the study.
11. Willing to have photographs and images taken of the treated areas to be used de-identified in evaluations, publications and presentations.

Exclusion Criteria

A subject is not eligible for participation in this study if he/she meets any of the following exclusion criteria:

1. History of hypertension, ischemic heart disease, valvular heart disease, congestive heart failure, pacemaker/defibrillator, abdominal aortic aneurism
2. Current hyperlipidemia, diabetes mellitus, hepatitis, liver disease, HIV positive status, blood coagulopathy or excessive bleeding, autoimmune or connective tissue disease
3. Having or undergoing any form of treatment for active cancer, or having a history of skin cancer or any other cancer in the areas to be treated, including presence of malignant or pre-malignant pigmented lesions
4. Having any active electrical implant anywhere in the body, such as a pacemaker or an internal defibrillator
5. Having a permanent implant in the treated area, such as metal plates or an injected chemical substance such as silicone
6. Having undergone any other surgery in the treated areas within 12 months of treatment or during the study, including liposuction
7. Previous body contouring procedures in the treatment area within 12 months
8. History of skin disease in the treatment area, known tendency to form keloids or poor wound healing
9. Suffering from significant skin conditions in the treated areas or inflammatory skin conditions, including, but not limited to, open lacerations or abrasions and active cold sores or herpes sores prior to treatment (duration of resolution as per the Investigator's discretion) or during the treatment course
10. Skin lesions in the treatment area other than simple nevi on physical examination (e.g., atypical nevus, tattoo, abrasions) including depressed scars in the treatment area

 Syneron Medical Ltd. Confidential	Clinical Study to Evaluate the Safety and Efficacy of the UltraShape Power Device Using the U-Sculpt Power Transducer for Abdominal Fat and Circumference Reduction			
	Protocol #	DHF21621	Rev. Date	April 05, 2016

11. Very poor skin quality (i.e., severe laxity)
12. Abdominal wall diastasis or hernia on physical examination
13. Abnormal kidney, liver or coagulation functions, abnormal lipid profile or blood count within the last 3 months
14. Obesity (BMI > 30)

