Figure 9: Patient positioning during circumference measurements (A) and measuring device position around the abdomen (B)

7. The measurement device should be activated at a constant tension to achieve an exact measurement of the circumference (use measurement device supplied by Syneron only).
8. In order to minimize measurement inaccuracies originating from human error, it is recommended that, whenever possible, the same operator re-measures the patient at approximately at the same hour of day (± 3 hours).
9. Patients should be under fasting for at least 3 hours prior to circumference measurement.

Treatment Procedure

Subjects will receive treatments with UltraShape Power device utilizing the U-Sculpt Power Transducer on the anterior abdomen.

Prior to each treatment measurements of weight, fat thickness (both by Ultrasound and Caliper), and abdominal circumference will be done according to the references from the enrollment visit (Baseline/ prior to Tx.1). Only patients who are eligible for treatment will be allowed to undergo the UltraShape Power procedure.

Enrolled subjects will undergo 3 successive bi-weekly (2 weeks interval) treatments (Tx.1, Tx.2 and Tx.3). Additional three (3) visits in the clinic will be occurred to follow-up the abdominal fat and circumference reduction at visits 4, 5 and 6 (4 weeks, 8 weeks and 12 weeks following last treatment).

 Syneron Medical Ltd. Confidential	Clinical Study to Evaluate the Safety and Efficacy of the UltraShape Power Device Using the U-Sculpt Power Transducer for Abdominal Fat and Circumference Reduction			
	Protocol #	DHF21621	Rev. Date	April 05, 2016

UltraShape Power Treatment Procedure

The subject abdomen will be gathered using reusable straps (supplied by Syneron Medical), to gather the fat area for treatment according to the instruction written in the User Manual.

According to size of the treatment area, the UltraShape Power device will determine the total number of FTZs to be delivered during treatment. While the recommended minimal number of ultrasound FTZs to be delivered per subject at a whole single treatment will be defined / determined by the system according to the subject physical characteristic and treated area size. Prior to admitting the FTZs (pulses) Parker acoustic gel will be applied and on the treated area and used as a coupler agent between the ultrasonic U-Sculpt Power Transducer and the skin surface.

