An adverse event (AE) is any adverse change in health or side effect that occurs in a study participant during their participation in the study.

Anticipated Adverse Effects

Following treatment with the UltraShape Power the following local adverse effects could occur (anticipated):

- Purpura
- Blister
- Bruising
- Bullae
- Erosion
- soreness
- First degree burn
- Second degree burn

An adverse event (AE) is any undesired clinical occurrence in a study subject as indicated by signs, symptoms, illnesses, events that develop or worsen in severity in association with the study when deemed by the Investigator to be related to use of the device or study procedures. The Investigator will document all adverse signs and symptoms regardless of severity or frequency that are either volunteered by subjects or observed during the course of the study that are related to the device. The Investigator will also record adverse experiences of subjects resulting from concurrent illnesses, reactions to concurrent medications, or progression of disease states that the Investigator deems related to the device. Included in the description will be the nature of the sign or symptom, the date of onset, whether the event was serious, the severity, the relationship to study procedures or investigational device, the action taken, the

 Syneron Medical Ltd. Confidential	Clinical Study to Evaluate the Safety and Efficacy of the UltraShape Power Device Using the U-Sculpt Power Transducer for Abdominal Fat and Circumference Reduction			
	Protocol #	DHF21621	Rev. Date	April 05, 2016

date of resolution, and the outcome. The Principal Investigator will determine the relationship of the adverse device effect to the investigational device.

Unanticipated Adverse Device Effects

For device studies, part 21 CFR 812.3(s) uses the term unanticipated adverse device effect which is defined as any serious adverse effect on health or safety or any life-threatening problem or death caused by, or associated with the device, if that effect, problem, or death was not previously identified in nature, severity, or degree of incidence in the investigational plan or application (including a supplementary plan or application), or any other unanticipated serious problem associated with a device that relates to the rights, safety, or welfare of subjects.

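### A device-caused skin lesion during the treatment course may cost a subject Tx.2 or Tx.3, and the replacement rule then makes that subject not evaluable, with no all-treated or safety set defined

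*Combined protocol and SAP*

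**What the plan says.** Under Inclusion Criteria and Exclusion Criteria, three items cannot be settled at enrolment:

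- Exclusion 9 covers "Suffering from significant skin conditions in the treated areas or inflammatory skin conditions, including, but not limited to, open lacerations or abrasions". Its time frame is before treatment, with resolution time left to the investigator, and it closes with "discretion) or during the treatment course".
- Exclusion 6 covers surgery in the treated areas "within 12 months of treatment or during the study, including liposuction".
- Inclusion 7 asks for a "negative urine pregnancy test as tested before each treatment and at the last visit", which falls 12 weeks after Tx.3.

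Three other sections bear on what follows from these items:

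- Anticipated Adverse Effects says that after treatment "the following local adverse effects could occur (anticipated", and lists blister, bullae, erosion, and first and second degree burn among them.
- Treatment Procedure, directly after the measurements required before each session, says "Only patients who are eligible for treatment will be allowed to undergo the UltraShape Power procedure".
- Subject Withdrawal and Replacement says "Subjects who fail to complete the treatment will be replaced and will not be evaluable". It also allows subjects who withdraw or are terminated to be replaced so that at least 120 complete.

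Neither Statistical Methods in the synopsis nor the Data Analysis section defines a safety population or an all-treated set.

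**The concern.** Entry criteria should describe a subject's status at entry. A criterion that stays open after the first session can be met because of the treatment under study. Exclusion 9 does this: its list of conditions is open-ended, it does not exempt lesions caused by the device, and the protocol expects the device to cause skin lesions in the treated area.

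Two results could be affected. The primary efficacy result is the change in ultrasound fat thickness from baseline to 12 weeks in a single arm. If subjects leave the evaluable set because they reacted to the device, that change describes only those who tolerated three sessions. The primary safety endpoint is the number, severity and type of adverse events. If its denominator is the evaluable set, the subjects most relevant to it are the ones left out.

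Exclusion 6 and inclusion 7 share the drafting fault, but surgery and pregnancy have no link to a device-caused lesion. They matter here for clarity only.

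**Working it through.** The plan states no figure on this point, so there is none to reproduce. The check sets the sections side by side and then gives an illustration of size.

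**The chain in the text**

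1. *Can the device cause the excluding condition?* Yes, by judgement. Exclusion 9 names neither blister nor erosion, but its list is open, and an investigator could reasonably judge an open erosion or a second degree burn in the treated area to be significant.
2. *Can that cost a session?* It may. Exclusion 9 runs through the treatment course, and the sentence in Treatment Procedure lets only subjects eligible for treatment proceed.
3. *What happens to a subject who misses Tx.2 or Tx.3?* Replacement and loss of evaluable status. The rule is mandatory, covers any reason, and is not limited to efficacy.
4. *Does any other section restore the subject to an analysis?* No. Events are recorded throughout, but no analysis set is named, so the denominator is open.
5. *Does the chain run after Tx.3?* No. Exclusion 9 ends with the treatment course and there is no session left to miss. Only the discretionary replacement of withdrawn or terminated subjects remains.

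**Size, under assumed rates**

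Let p be the share of treated subjects stopped before Tx.3 by a device-caused lesion. The documents give no value, so 1% to 10% is assumed. The target of 120 completers comes from Subject Withdrawal and Replacement. Number to treat = 120/(1 − p), rounded up; number replaced = that number minus 120; chance of at least one case among 120 treated = 1 − (1 − p)^120.

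| Assumed p | Treated | Replaced | Chance of at least one case in 120 |
|---|---|---|---|
| 1% | 120/0.99 = 121.2, so 122 | 2 | 70% |
| 2% | 120/0.98 = 122.4, so 123 | 3 | 91% |
| 5% | 120/0.95 = 126.3, so 127 | 7 | 99.8% |
| 10% | 120/0.90 = 133.3, so 134 | 14 | about 100% |

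**Effect on a reported rate**

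Suppose 12 subjects are stopped and replaced to reach 120 completers. Then 120 + 12 = 132 were treated.

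- All-treated rate: 12/132 = 9.1%.
- Summary limited to completers: all 12 are absent. If no completer had such a lesion, it would show 0/120, with exact two-sided 95% upper limit 1 − 0.025^(1/120) = 3.0%.

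The second line is the extreme. A lesion judged not significant, or arising after Tx.3, costs no session and would still be counted among the completers.

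**The case against.** The strongest counter-argument is that eligibility is assessed once. Enrollment and Screening places the review of criteria at the first visit, and Table 3 marks eligibility screening only in the first column. The sentence in Treatment Procedure can then be read as a gate on the session, resting on such things as the fat-thickness condition under Measurements, and not as a renewed test of participation. This stands in part: the documents do not say outright that a later eligibility failure removes anyone. But a session gate is enough for the chain, because a missed session triggers the replacement rule.

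The second argument is that adverse events are not lost. Primary Safety Endpoint, Table 2, Post Treatment Procedures and the Safety paragraph of Data Analysis all call for recording throughout the study, with no restriction to evaluable subjects. This stands, and it confines the problem to the analysis sets.

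The third is that the harm comes from the replacement rule and not from the criteria. A subject who misses Tx.2 because of a burn is not evaluable whatever exclusion 9 says. This also stands: removing the on-study phrases from the three criteria would leave the selection in place.

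A reader might also infer two stronger things. One is that a subject who completed all treatments could be discarded after the 12-week data exist, because of a late positive pregnancy test or surgery. No text attaches that consequence to late ineligibility. The other is that the trial would report no device lesions at all. That requires every case to be judged significant, to cost a session and then to be left out of safety reporting, and the documents establish only that this is possible.

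**Conclusion.** The point holds in a limited form. Three entry criteria contain on-study conditions, and through exclusion 9 and the replacement rule a device-caused lesion may remove a treated subject from the evaluable set. The 12-week efficacy sample is then selected on a post-treatment event, and the safety denominator may leave out the affected subjects.

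The conclusion rests on two readings: that an investigator may judge such a lesion significant under exclusion 9, and that the lack of any defined safety or all-treated set leaves the scope of not evaluable open. The size is unknown. Across the assumed 1% to 10%, between 2 and 14 treated subjects would be replaced to reach 120 completers. The contrast of 9.1% (12/132) with 0/120 marks the outer edge and is not a forecast.

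The correction should be made, since it concerns a stated rule that selects on outcome and costs no data. The main repair belongs in the replacement rule and the analysis section; the wording of the criteria is secondary.

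**What to change.** 1. In Data Analysis, state that every subject who receives Tx.1 stays in the safety summary and in an all-treated efficacy summary, whether or not replaced. Amend the not-evaluable sentence in Subject Withdrawal and Replacement to match, and present any completer analysis as supportive.
2. State that a skin condition, surgery or pregnancy arising after Tx.1 is recorded as an adverse event or protocol event, and is not a retrospective entry failure.
3. For clarity, apply the entry criteria at enrolment. List the pregnancy tests and skin checks before Tx.2, before Tx.3 and at the last visit as on-study procedures.

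The Inclusion and Exclusion Criteria, Subject Withdrawal and Replacement, and Treatment Procedure must be reconciled on what applies once treatment has started. Whether a given session should go ahead is a clinical matter on which no view is taken here.

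The cost is a few sentences in the analysis and replacement sections and a tidying of three criteria. No extra data collection is needed: weight, fat thickness, circumference and safety are already scheduled at the follow-up visits.

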1. Statistically significant abdominal fat reduction post UltraShape Power treatments as measured by Ultrasound device at Pre Tx.3, 4 weeks, and 8 weeks follow-up (4wk FU and 8wk FU) versus baseline.
2. Statistically significant abdominal fat reduction post UltraShape Power treatments as measured by calibrated Caliper at Pre Tx.2, Pre Tx.3, 4 weeks, 8 weeks and 12 weeks follow-up (4wk FU, 8wk FU and 12wk FU) versus baseline.
3. Statistically significant abdominal circumference reduction post UltraShape Power treatment/s at Pre Tx.2, Pre Tx.3, 4 weeks, 8 weeks and 12 weeks follow-up (4wk FU, 8wk FU and 12wk FU) versus baseline.
4. Investigator satisfaction:
Satisfaction assessment will be performed by the study investigator using a pre-defined scale questionnaire. The investigator will answer this questionnaire at each follow-up visit (4wk FU, 8wk FU and 12wk FU).
5. Subject improvement and satisfaction:
Improvement and satisfaction assessment will be performed independently by the subject himself using a pre-defined scale questionnaire. The subjects will answer this questionnaire at each follow-up visit (4wk FU, 8wk FU and 12wk FU).

Primary and Secondary Efficacy Endpoint

Primary and secondary objectives will be measured using the next efficacy endpoints:

1. Fat thickness measurements using Ultrasound device
2. Fat thickness measurements using calibrated Caliper
3. Circumference measurements of the abdominal area using Measuring Tape
4. Investigator satisfaction using a pre-defined scale
5. Subject improvement and satisfaction using a pre-defined scale
6. Photography

 Syneron Medical Ltd. Confidential	Clinical Study to Evaluate the Safety and Efficacy of the UltraShape Power Device Using the U-Sculpt Power Transducer for Abdominal Fat and Circumference Reduction			
	Protocol #	DHF21621	Rev. Date	April 05, 2016

Primary Safety Endpoint

The number, severity and type of any adverse event recorded throughout the study and post treatment (discomfort (pain), immediate and delayed response).

1. Occurrence of expected post treatment immediate response including erythema and edema and during all study period based on predefined scale (Table 4).
2. Number, severity and type of any adverse event recorded throughout the course of the study.

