Perform the UltraShape Power utilizing the U-Sculpt Power Transducer treatment according to the instruction in the User Manual.

Expected post treatment side effects are limited to Erythema (blanchable/non-blanchable), Edema, Heat sensation and pain sensation.

Post Treatment Procedures

1. Pain assessment – immediately after each treatment the subjects will be asked to rank the pain sensation during treatment using Numerical Scale Response (NSR; see Appendix III) for the UltraShape Power procedure
2. Safety aspect will be assessed before and after each treatment:
 - a. Clinical effects - All visible and palpable immediate response will be recorded for the entire treatment area using a 4-point severity scale (Table 4)
 - b. Adverse Events – Record the number, severity and type of any adverse event occurred before, through and after treatments.

Return Visits

All subjects will be requested to return to the clinic at the following time-points during the study in order to assess the clinical performance of the device:

- Visit 4: FU1 – 4 weeks (± 7 days) post last treatment.
- Visit 5: FU2 – 8 weeks (± 7 days) post last treatment.
- Visit 6: FU3 – 12 weeks (± 7 days) post last treatment.

At each return visit the following procedures will be conducted and data recorded:

- Weight.
- Ultrasound fat-thickness measurements.
- Caliper fat-thickness measurements.
- Circumference measurements.

SYNERON CANDELA Syneron Medical Ltd. Confidential	Clinical Study to Evaluate the Safety and Efficacy of the UltraShape Power Device Using the U-Sculpt Power Transducer for Abdominal Fat and Circumference Reduction			
	Protocol #	DHF21621	Rev. Date	April 05, 2016

- Skin assessment for clinical effects due the procedures:
 - Post treatment response and adverse events.
- Photographs as conducted at baseline.
- Satisfaction questionnaire performed by the investigator using the Global Aesthetic Improvement (GAI).
- Completion of the Subject Follow Up questionnaire:
 - Subjective Improvement and satisfaction performed by the subject using the Global Aesthetic Improvement (GAI).
- At the final visit a urine pregnancy test will be performed for women with bearing potential.

DATA ANALYSIS

Recording

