Significant device failure may constitute an adverse event if an undesirable experience occurs. This definition includes any event resulting from insufficiencies or inadequacies in the instructions for use or the deployment of the device, or any event that is a result of a user error.

All unanticipated adverse effects will be graded as follows:

Mild: Sign or symptom, usually transient, non-life-threatening requiring no special treatment and generally not interfering with usual activities.

Moderate: Sign or symptom, non-life-threatening which may be ameliorated by simple therapeutic measures, and may interfere with usual activity.

Major: Sign or symptom that is intense or debilitating but non-life-threatening and that interferes with usual activities. Recovery is usually aided by therapeutic measures and the discontinuation of the study device may be required.

Severe: Any untoward medical occurrence that at any time results in death or life-threatening illness, resulting in persistent or significant disability/incapacity.

The relationship of the adverse effect to the study is defined as follows:

Probable: An adverse event has a strong temporal relationship to study device, and another etiology is unlikely or significantly less likely.

Possible: An adverse event has a strong temporal relationship to the study device, and an alternative etiology is equally or less likely compared to the potential relationship to study device.

Probably not: An adverse event has little or no temporal relationship to the study device and/or a more likely alternative etiology exists.

Not related: An adverse event has no temporal relationship to study device or has a much more likely alternative etiology.

 Syneron Medical Ltd. Confidential	Clinical Study to Evaluate the Safety and Efficacy of the UltraShape Power Device Using the U-Sculpt Power Transducer for Abdominal Fat and Circumference Reduction			
	Protocol #	DHF21621	Rev. Date	April 05, 2016

Reporting Adverse Events (AE) and Serious Adverse Events (SAE)

Anticipated Adverse Events: Anticipated adverse events in this study include Purpura, blistering, bruising, bullae, erosion, soreness and burn. If an unanticipated adverse event occurs at any time during or after the use of the UltraShape Power device, the Investigator must report it to Syneron.

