The Investigator must report all unanticipated adverse device effects that are serious in nature to the clinical study monitor immediately or within twenty-four hours by telephone (see below). If such an unanticipated adverse device effect is reported after normal working hours, the Investigator will leave a voice message at the monitor’s telephone number with accompanying report of the unanticipated adverse device effect faxed or sent to the fax number/e-mail address below:

[name], Global VP of Clinical Affairs
Telephone/Fax No.: From the U.S. [name]
[name] (cell)
E-mail: [contact]

A written report prepared by the Principal Investigator must follow within five working days to both the IRB and to Syneron and should include a full description of the event and sequence.

Measures taken to protect the rights and welfare of subject

Research records will be available to study personnel, the sponsor, Ethics Review Committee and regulatory agencies as required. Research records may be used for purposes of medical education, after removal of subject names or other identifying information. In the ICF the subjects will be informed that the photographs and video taken of them during the study may be made available to the sponsor for marketing and instructional purposes, after removal of identifying information. All images collected will be stored without personal subject identifiers at the site and at Syneron.

RISK/BENEFIT ANALYSIS

Risks

Syneron has determined that the *UltraShape Power* system is non-significant risk device. As indicated in the AE section, the anticipated risks associated with the use of both of the systems are:

- Purpura
- Blister
- Bruising
- Erosion
- soreness
- First degree burn

 Syneron Medical Ltd. Confidential	Clinical Study to Evaluate the Safety and Efficacy of the UltraShape Power Device Using the U-Sculpt Power Transducer for Abdominal Fat and Circumference Reduction			
	Protocol #	DHF21621	Rev. Date	April 05, 2016

- Bullae
- Second degree burn

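### Whether expected redness and swelling also count as adverse events depends on which section a site follows, so the adverse event count is not comparable across sites

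*Combined protocol and SAP*

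**What the plan says.** Five places in the protocol bear on this.

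- **UltraShape Power Treatment Procedure.** "Expected post treatment side effects are limited to Erythema (blanchable/non-blanchable), Edema, Heat sensation and pain sensation". The wording is closed: nothing else is expected.
- **Anticipated lists.** The section Anticipated Adverse Effects lists purpura, blister, bruising, bullae, erosion, soreness, and first and second degree burn. The reporting section summarises this: "Anticipated adverse events in this study include Purpura, blistering, bruising, bullae, erosion, soreness and burn". The Risks section repeats the eight items after the words "As indicated in the AE section, the anticipated risks associated with the use of both of the systems are". None of the three names erythema, edema or heat.
- **Primary Safety Endpoint.** Item 1 is "Occurrence of expected post treatment immediate response including erythema and edema", rated on Table 4. Item 2 is "Number, severity and type of any adverse event recorded throughout the course of the study". The items are separate, but the sentence introducing them describes the adverse events to be counted as taking in pain and both immediate and delayed reactions.
- **Post Treatment Procedures.** Item 2a sends every visible or palpable immediate reaction to Table 4. Item 2b records adverse events separately. No rule connects the two.
- **Adverse Events (AE).** An adverse event is "any adverse change in health or side effect that occurs in a study participant". The same section has the investigator document device-related signs and symptoms however mild or infrequent they are.

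**The concern.** The number, severity and type of adverse events is a primary safety endpoint. A count pooled over up to 10 sites is interpretable only if every site enters the same finding in the same way.

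Here a site that follows the item 1 and item 2 split can score post-treatment redness on Table 4 and stop. A site that follows the adverse event definition, or the lead-in to the endpoint, will score it on Table 4 and also enter an adverse event. Each is applying protocol text. If the reaction is common, it could dominate the adverse event count, and differences between sites would reflect recording practice rather than the device.

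**Working it through.** There is no figure in the plan to reproduce: it gives no expected rate of erythema or of adverse events, and no safety threshold. The check is a comparison of text, followed by a bound on the size.

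**Step 1: the lists side by side.**

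| Reaction | Expected list (treatment section) | Anticipated lists (adverse event, reporting, risk sections) | Scale named for it |
|---|---|---|---|
| Erythema | yes | no | Table 4 |
| Edema | yes | no | Table 4 |
| Heat sensation | yes | no | none named |
| Pain | yes | soreness is listed | NSR (Appendix III) |
| Purpura, blister, bruising, bullae, erosion | no | yes | none named individually |
| Burn | no | yes | none named individually |

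The mismatch runs both ways. Three expected reactions are missing from the anticipated lists, and a closed expected list excludes effects that the other sections anticipate. No sentence links *expected* to *anticipated* or says that they are different tiers.

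**Step 2: is an expected reaction an adverse event?** Two readings are available.

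- *No.* The endpoint numbers the Table 4 response and adverse events as items 1 and 2. Post Treatment Procedures separates them as 2a and 2b, and Table 2 gives them separate rows and tools.
- *Yes.* The treatment section calls these reactions side effects, and the definition makes a side effect an adverse event. The documentation duty has no severity floor. The endpoint's lead-in puts immediate and delayed reactions within the adverse event count. The Treatment Visit paragraph under Data Analysis uses skin assessments and pain scores to document adverse events.

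Timing does not separate the readings, because item 1 covers the whole study period as well as the immediate response.

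**Step 3: does the route affect severity too?** Table 4 runs from 0 to 3, and its top grade, severe, has no further definition. The other scale runs mild, moderate, major, severe, and there severe means death, life-threatening illness or disability. That scale is stated only for unanticipated effects. The two sets of grades cannot be merged without showing which scale each came from.

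**Step 4: size.** Let N = 120 subjects and p = the share with at least one such reaction. The largest possible difference in subjects with an adverse event is N × p, reached when all sites follow one reading rather than the other and the affected subjects have no other adverse event.

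- p = 10% (assumption): 120 × 0.10 = 12 subjects.
- p = 100% (assumption): 120 × 1.00 = 120 subjects.

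A mixture of readings across sites, or other adverse events in the same subjects, gives a smaller difference.

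**The case against.** The strongest reply is that nothing goes missing. Table 4 scoring of visible and palpable reactions is required after every treatment, so erythema and edema are captured whatever a site does with the adverse event form. The plan has no safety hypothesis, comparator or threshold, so no stated decision turns on the count. Events outside the overlap, such as blisters, are unaffected. All of this stands. It limits the point to the adverse event tally and its comparability between sites; it does not supply the missing rule.

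A reader might infer more than the documents support:

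- *That redness becomes an unanticipated event.* The reporting section gives the anticipated list and then requires unanticipated adverse events to be reported to the sponsor, so a literal reader could take this route. But that list is introduced with open wording, and the formal definition of an unanticipated adverse device effect needs a serious effect, or another serious problem, not already identified in the plan. The plan itself names these reactions as expected.
- *That the investigator can choose one form instead of the other.* The Table 4 entry is mandatory. Only the additional adverse event entry is open.
- *That all four expected reactions are Table 4 items.* Item 1 names erythema and edema. Pain is rated on the NSR, and heat sensation is assigned to no named scale.
- *That the reporting section's unqualified mention of burn is a further contradiction.* It reads naturally as a summary of the fuller list, and the point does not rest on it.

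**Conclusion.** The concern holds for the adverse event count. The expected list and the anticipated lists contradict each other, and the text supports both counting and not counting an expected erythema or edema response as an adverse event. That part of the primary safety endpoint is therefore not comparable across up to 10 sites.

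Up to 12 to 120 of 120 subjects could change status on identical observations. This is a ceiling, and it rests on an assumed rate of 10% to 100% because the documents give none. It does not follow that reactions would go unrecorded, that the whole adverse event profile is uninterpretable, or that these reactions meet the formal definition of an unanticipated device effect. The correction should be made because it is cheap and concerns a primary safety endpoint.

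**What to change.** 1. **Analysis.** Report local skin reactions in one table by term at subject level: subjects with any occurrence, and worst grade with its source scale shown. Pool the Table 4 entries and the adverse event form entries, so that the choice of form cannot change the result.
2. **Wording.** Reconcile the Primary Safety Endpoint, the treatment and post-treatment sections, the adverse event definition and anticipated list, the reporting section and the Risks section, so that the expected and anticipated lists no longer contradict each other. The lists need not be identical; two tiers can stay if the text says how they relate. State one rule, confirmed by the sponsor, on whether a Table 4 response is also entered as an adverse event. No clinical threshold is proposed here.

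The cost is protocol wording and one additional safety table. No new measurement or visit is needed.
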